8.5 LEROS and NH matched datasets

In order to optimize the comparability of patient data in the NH control set and the LEROS ITT population, subsets from the NH control set will be prospectively defined. These subsets will be matched separately for all the efficacy analyses using the matching rules defined in section 8.5.1 and 8.5.2.

A total of 8 datasets (as exemplified in Table 8-1) will be generated based on the matching algorithm (taking in consideration time since symptoms onset at BL and follow-up in analysis).

Table 8-1- LEROS and NH matched datasets

time since symptoms onset	follow-up (months)				
≤1 year	6	12	18	24	
> 1 year	6	12	18	24	

8.5.1 Matching algorithm for the primary endpoint

The external NH control set for the eyes with BL \leq 1 year since onset of symptoms in the LEROS ITT population will be generated as follows (section 19.1 presents the matching algorithms using workflow diagrams and provides examples of matched BL and follow-up visits):

1. Since there is no treatment to be considered in the NH control set, in principle any VA observation at any time point after the onset of symptoms in any eye can be used as a BL for that eye. The primary outcome measure in LEROS is the VA at 12 months after BL. Therefore, using a "window" of ±3 months, any eye with a VA observation at any time point in the NH control set which has a follow-up VA assessment within

SNT-IV-005 Statistical Analysis Plan

Confidential

12±3 months will be retained for use as a possible BL observation. All such possible BL observations and subsequent VA assessments will form the NH control subset to be compared to the BL of LEROS.

- 2. In LEROS, the average time from the onset of symptoms to the start of Raxone® treatment will be calculated once all data is available. The start of the Raxone® treatment will be used as the BL in the statistical analyses.
- 3. For each VA observation retained in the NH control subset, the time from the onset of symptoms at each possible BL time point will be calculated for each eye.
- 4. For each eye in the NH control subset, the VA observation for which time since onset of symptoms is closest to the average time since onset of symptoms at BL calculated for LEROS (see 2) will be selected as the BL VA observation for that eye. Any eye in the NH control subset with a BL VA observation >6 months after the average time since onset of symptoms at BL in LEROS will be discarded. The resulting dataset will form the "final NH control subset" to be used for the primary endpoint. In this way, BL observations in the final NH control subset will be closely matched to the BL in the LEROS ITT population.
- 5. The change from BL in VA at 12±3 months for each eye in the final matched NH control subset will be compared to the change from BL visit to the visit scheduled at Month 12 in LEROS.

This algorithm will guarantee that the time from the onset of symptoms to the BL assessment is comparable between the final NH control dataset and LEROS.

The described process will be repeated for the secondary analyses applied for the 6, 18 and 24 month time points for the eyes with $BL \le 1$ year after the onset of symptoms.

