1.1 Background

Leber's Hereditary Optic Neuropathy

LHON is a maternally inherited loss of vision due to atrophy of the optic nerve. More than 90% of individuals with LHON harbour one of three point mutations in mitochondrial DNA (mtDNA) (G11778A, T14484C, G3460A) affecting genes encoding complex I subunits of the respiratory chain (Mackey 1996, Newman 2013). It typically presents in young adults, mostly men, as painless acute or subacute visual failure of both eyes in quick succession. The estimated prevalence is approximately 2.2 per 100,000 (Mascialino et al., 2012) and LHON is thus an Orphan Disease according to EU and US criteria. Clinically, the acute phase of the disease begins with blurring of central vision and colour de-saturation that affect both eyes. After the initial symptoms, both eyes are usually affected within two to four months from disease onset. Within 12 months of visual loss in one eye, over 97% of patients will have second eye involvement. The central visual acuity deteriorates to the level of counting fingers in up to 80% of cases. Following the nadir, acuity may improve. The degree of improvement is dependent, in part, also on the precise genetic mutation of affected patients. With disease progression, individuals then proceed into the atrophic phase and are usually legally blind for the rest of their lives with a permanent large centrocecal scotoma (Sadun et al., 2011).

Idebenone 2-(10-hydroxydecyl)-5,6-dimethoxy-3-methyl-cyclohexa-2,5-diene-1,4-dione has been suggested to be effective in by-passing the complex I deficiency resulting from the mtDNA point mutations and maintaining cellular energy production by stimulating the alternative pathway through complexes II and III (Haefeli et al., 2011). This activity may also reduce the production of reactive oxygen species (ROS) associated with complex I deficiency and to protect cell membranes and mitochondria from oxidative damage. This provides a strong rationale for its use in LHON (summarized in Gueven and Faldu, 2013; Gueven, 2014).

Detailed information on the medicinal product and on non-clinical data is available in the Investigator's Brochure (IB).

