- Since there is no treatment to be considered in the combined CRS, in principle any VA observation at any time point after the onset of symptoms in any eye can be used as a Baseline for that eye. The primary outcome measure in the open label study is the VA at 12 months after Baseline. Therefore, using a "window" of ±3 months, any eye with a VA observation at any time point in the combined CRS control dataset which has a follow-up VA assessment within 12±3 months will be retained for use as a possible Baseline observation. All such possible Baseline observations and subsequent VA assessments will form the CRS control dataset subgroup to be compared to the Baseline of the open label study.
- 2. In the open label study, the average time from the onset of symptoms to the start of idebenone treatment will be calculated once all data is available. The start of the idebenone treatment will be used as the Baseline in the statistical analyses.
- 3. For each VA observation retained in the CRS control dataset subgroup, for each eye the time from the onset of symptoms at each possible Baseline time point will be calculated.

- 4. For each eye in the CRS control dataset subgroup, the VA observation which is closest in time since the onset of symptoms to the average time since onset of symptoms at Baseline calculated for the open label study (see 2) will be selected as the Baseline VA observation for that eye. Any eye in the CRS control dataset subgroup with a time since onset >6 months after the average time since onset at Baseline in the open label study will be discarded. The resulting data set will from the "final CRS control dataset". In this way, Baseline observations in the final CRS control dataset will be closely matched to the Baseline in the open label study.
- 5. The change from Baseline in VA at 12±3 months for each eye in the final CRS control dataset selected as described for the primary endpoint will be compared to the change from the Baseline visit to the visit scheduled at Month 12 in the open label study.

This algorithm will guarantee that the time from the onset of symptoms to the Baseline assessment is comparable between the final CRS control dataset and the open label study.

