As SNT-CRS-002 study was completed (Clinical Study Report version 1.0 dated 15 July 2019), the data collected in the natural history studies has now been checked for the estimate of the responder rate. Based on the combined data from 175 eyes in the two natural history studies (SNT-IR-006 and SNT-CRS-002), the estimated responder rate is below 22%, i.e. lower than the initially expected rate of 24%. Although the determination of the exact responder rate for the natural history studies requires final data from the LEROS study for matching purposes, it is reasonable to assume that the responder rate of the natural history studies is not higher than 22%. The sample size for LEROS study is therefore re-calculated using the same methods as in the original protocol (Version1.0, 29 January 2016). In order to reach a power of 90% for the comparison of the responder rates between the natural history studies (assumed to be 22% instead of 24%) and the LEROS study (assumed to be 40%, as defined in the protocol), evaluable data from altogether 110 eyes from the LEROS study is required. In order to account for a drop-out rate of 30% (as defined in the protocol), at least 80 patients (equal to 160 eyes) will be enrolled to the LEROS study.

The sample size calculation was done with nQuery Advisor version 8.3.

For the sample size for the eye treated >1 year after the onset of symptoms and the corresponding external natural history control group, the aim is to collect VA data from same number of eyes as for the primary objective in order to compare the patients treated ≤1 and >1 year since the onset of symptoms and to compare patients treated with Raxone >1 year since the onset of symptoms with the corresponding natural history control group, assuming sufficient natural history control data can be collected to generate the natural history control group as described in 8.3.2.

Study: SNT-IV-005

V1.0 07 June 2021

7 Statistical hypotheses

The primary aim of the analysis is to show the superiority of Raxone® (patients treated ≤1 year after onset of symptoms) versus matching NH IDE naïve patients in proportion of eyes with clinically relevant recovery of VA from BL or 12 month maintenance of BL VA better than 1.0 logMAR

H₀: Raxone® (patients treated ≤1 year after onset of symptoms) is not superior to matching NH IDE naïve patients in proportion of eyes with CRR of VA from BL or 12 month maintenance of BL VA better than $1.0 \log MAR$

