 H_1 : Raxone® (patients treated ≤ 1 year after onset of symptoms) is superior to matching NH IDE naïve patients in proportion of eyes with CRR of VA from BL or 12 month maintenance of BL VA better than $1.0 \log MAR$

A two-sided 95% confidence interval (CI) for the odds ratio (Raxone® versus NH IDE naïve) is used in the evaluation of the hypotheses. Superiority is shown if the lower limit of the two-sided 95% CI is greater than 1. This is equivalent to obtaining a p-value of less than 0.05 in the statistical test for the H_0 .

8 Analysis sets

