In the statistical analyses a p-value less than 0.05 will be considered as statistically significant. If not stated otherwise, all tests will be performed as two sided tests and two sided 95% confidence intervals will be produced for the treatment differences.

CRS-1, CRS-2 and LEROS data will be presented in separate listings (one per study).

Unscheduled or repeat assessments in LEROS will not be included in summary tables, but will be included in listings.

Otherwise specified, listings will be sorted by patient number and visit date.

Deviations from the statistical plan will be reported in the clinical study report, including the rationale for the deviation.

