12.1 Primary endpoint

Endpoint: Proportion of eyes with clinically relevant recovery (CRR) of visual acuity from Baseline (BL) or in which BL VA better than 1.0 logMAR was maintained at Month 12 in patients treated with Raxone® ≤1 year after the onset of symptoms, compared to matching external natural history control group. CRR definition is presented in section 16.

Analysis sets: Primary endpoint analysis will use all LEROS mITT eyes that are ≤1 year since onset of symptoms at BL and have the Month 12 assessment. External NH control set is generated as described in section 8.5.1 (Matching algorithm for the primary endpoint), using VA assessments within 12±3 months from BL.

Analysis method: The primary endpoint will be analysed using a logistic regression model. The binary response will be used as the dependent variable. The independent variables include the treatment group (Raxone® treated patients versus untreated control group), gender (male, female) and mutation group (G11778A, G3460A, T14484C) as fixed factors.

The difference between the Raxone® treated patients versus NH group will be estimated with odds ratio, two-sided 95% confidence intervals and two-sided p-values

```
proc logistic;
  class treatment gender mutation / param=ref;
  model CRB(event='1') = treatment mutation gender / link=logit clodds=pl;
  oddsratio treatment;
run;
```

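### Choosing control baselines nearest one LEROS mean does not match time since onset, and the primary model does not adjust for it

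*SAP*

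**What the plan says.** SAP 8.5.1 and Protocol 9.2.1 use the same algorithm. The average time from onset to start of treatment is computed for LEROS once all data are in. Each control eye then contributes one baseline, the eligible record whose time since onset "is closest to the average time since onset of symptoms at BL calculated for LEROS". The only exclusion on timing is on the late side; in the Protocol's wording, a control eye "with a time since onset >6 months after the average time since onset at Baseline in the open label study will be discarded". The SAP then asserts: "This algorithm will guarantee that the time from the onset of symptoms to the BL assessment is comparable".

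On the LEROS side, SAP 12.1 keeps every mITT eye that is at or below 1 year since onset and has a Month 12 assessment, each at its own time since onset. The model is a logistic regression: "The independent variables include the treatment group", followed by gender and mutation. Protocol 9.4.2 has treatment and mutation only. Superiority is decided on this odds ratio (SAP section 7): "Superiority is shown if the lower limit of the two-sided 95% CI is greater than 1".

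Time since onset does appear elsewhere. It is in the propensity score of the inverse-probability-weighted sensitivity analysis (SAP 12.1.1), and Tables 11-1 and 11-2 tabulate it for the matched sets.

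**The concern.** The endpoint is measured from baseline, so the untreated response rate may depend on where in the disease course the baseline falls. The sponsor's own text makes this plausible. Protocol 1.1 describes a fall in acuity and then says "Following the nadir, acuity may improve". SAP 12.4 states that progression is not linear. The stabilization part of the endpoint is open only to eyes still better than 1.0 logMAR at baseline. Protocol 2.1.2 makes the influence of time since onset on recovery a secondary objective.

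There is no randomization, so comparability rests on the matching rule and the model. If the two groups are observed over different parts of the natural course and the model has no term for this, the odds ratio can depart from 1 with no drug effect. It could create a superiority claim or hide a real effect.

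**Working it through.** **1. The plan's own figure.** Inputs from SAP section 6: 22% v 40% responders, 175 control eyes, 110 LEROS eyes, 90% power. From SAP section 9: two-sided 0.05.
- Pooled rate = (110×0.40 + 175×0.22)/285 = 0.2895.
- Null SE = √[0.2895×0.7105×(1/110 + 1/175)] = 0.0552.
- Alternative SE = √(0.40×0.60/110 + 0.22×0.78/175) = 0.0562.
- Power = Φ[(0.18 − 1.96×0.0552)/0.0562] ≈ 0.90.

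The figure reproduces, treating eyes as independent. It does not depend on the matching rule, so nothing below alters a stated number.

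**2. What the rule does to time since onset.** The documents give no distribution of onset times or control visit patterns, so those used here are assumptions. I also take the LEROS average to be over the ≤1-year eyes, which step 2 does not say outright. With LEROS uniform over 0 to 12 months (mean 6.0, SD 3.5), the selection rule gives:

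| Assumed control visits | Control mean | Control SD |
|---|---|---|
| every 2 months, first at 0-3 | 5.9 | 1.4 |
| every 6 months, first at 0-6 | 5.1 | 2.0 |
| every 4 months, first at 2-14 | 7.6 | 2.4 |

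With frequent visits the means agree but the spreads do not. With sparse or late visits the means differ too. If the LEROS mean is 4.0, the third pattern gives a control mean of 6.1.

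**3. The upper limit.** The latest admissible control baseline is the LEROS mean plus 6 months. It passes 12 months as soon as the mean passes 6; a mean of 7.5 gives 13.5. With an assumed LEROS mean of 8.0, the three patterns put 1%, 4% and 17% of control baselines beyond 12 months.

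**4. Effect on the comparison, no drug effect, 110 v 175 independent eyes.** Use the first row of the table and let p(t) be the untreated response.
- U-shape, p(t) = 0.15 + 0.15[(t−6)/6]². LEROS: 0.15 + 0.15/3 = 0.200. Controls: E(t−6)² = 1.4² + 0.1² = 1.97, so 0.15 + 0.15×1.97/36 = 0.158. False difference +4.2 points; two-sided type I error about 15%.
- Hump, p(t) = 0.30 − 0.20[(t−6)/6]². LEROS 0.233, controls about 0.29. False difference −5.6 points; about 18%.
- Linear in t, either slope: difference about 0; 5.0%.

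Over all 36 combinations (three LEROS distributions, three visit patterns, four curves) the false difference ranged from −5.6 to +4.2 points and two-sided type I error from 5% to 18%.

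**5. Whether adjustment repairs it.** Take controls normal with mean 6 and SD 1.5, so E(t−6)²/36 = 2.25/36 = 0.0625.
- U-curve rising by 0.15 at the ends: 0.200 v 0.159, OR = 0.250/0.190 = 1.32.
- U-curve rising by 0.25 at the ends: 0.233 v 0.166, OR = 0.304/0.199 = 1.53.

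The chance of wrongly declaring superiority is about 14% and 28-29%, against a nominal 2.5%. Adding linear and quadratic time since onset brought it to about 2.5% to 3.6% in simulation.

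**6. What adjustment costs.** Same control pattern, true rates 22% v 40%, no dependence on time: power is about 90% unadjusted and about 77% with linear plus quadratic terms. With less bunching (control SD 2.0 to 2.5) it is 83% to 87%.

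**The case against.** Several points against the concern stand.

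- **The plan does not ignore time since onset.** The weighted sensitivity analysis uses it together with age and baseline acuity, a broader set than proposed here. Tables 11-1 and 11-2, with shell 19-1, show its mean, SD and quartiles side by side, so an imbalance would be visible. What they lack is force: section 7 decides superiority on the model's odds ratio, no rule covers disagreement with the weighted analysis, and no balance criterion is set.
- **The size depends on assumed curves.** With bunched controls and a linear response there is no bias. A reader might infer from the 28-29% figure that false superiority is likely, or that the bias favours the drug. The documents support neither; they contain no response curve, and a hump shape reverses the sign.
- **The one-sided discard matters little.** A reader might infer that keeping early records makes controls systematically earlier than LEROS. A symmetric lower limit would be the mean minus 6 months. That removes nothing if the mean is at or below 6, and only records before 1.5 months if the mean is 7.5. LEROS also admits eyes from onset onward.
- **The 12-month overrun is conditional.** It needs a LEROS mean above 6 months, which is not given. The selection workflow in SAP 19.1 is a figure not available here and may contain a limit that the text of step 4 omits.
- **Adjustment is not free**, as step 6 of the working shows.

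**Conclusion.** The concern holds in a limited form. Selecting control baselines nearest one mean does not match the distribution of time since onset, does not secure equal means when control visits are sparse, and as written allows control baselines beyond the 1-year limit that LEROS eyes must meet. The comparability guarantee is therefore not earned. Because the deciding model has no term for time since onset, its odds ratio can be biased in either direction.

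This requires untreated response to vary with time since onset, and, where the means agree, to vary non-linearly. The described disease course makes that plausible without quantifying it. The range in step 4 of the working illustrates the exposure and does not estimate the bias in this trial; it rests on assumed onset distributions, visit patterns and response curves, and on independent eyes.

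This should be fixed: the weakness sits in the analysis that decides superiority, and the needed variable is already derived.

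**What to change.** - **SAP 12.1:** add each eye's own months since onset at baseline, linear plus quadratic, to the primary logistic model. This uses two degrees of freedom. Narrow categories are less suitable: with a control SD of 1.5 around 6 months, only about 4 of 175 control eyes would fall in each outer quarter of the year (175×0.023).
- **SAP 8.5.1, step 4:** admit a control baseline only if it is at or below 1 year after that eye's onset.
- **SAP 8.5.1, closing sentence:** replace the guarantee with a reference to the time-since-onset comparison already planned in Tables 11-1 and 11-2.
- **SAP section 14:** record the departure from the protocol's model and algorithm, and make the change before database lock.

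The main cost is precision: up to about 13 points of power (90% to about 77%) if control baselines bunch tightly round the mean, less otherwise. A few control eyes may be lost, and only if the LEROS mean exceeds 6 months.

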8.5.2 Matching algorithm for the secondary endpoints

The external NH control set for the eyes with BL >1 year since onset of symptoms in the LEROS ITT population will be generated as follows (section 19.1 presents the matching algorithms using workflow diagrams):

SNT-IV-005 Statistical Analysis Plan

Confidential

- 1. All available eyes in the external NH control set will be considered, regardless of whether the eye in question was used in the control group for the primary objective or not.
- 2. All VA assessments >1 year after the onset of symptoms are considered as potential BL values.
- 3. If a potential BL value does not have a follow-up VA assessment within 12±3 months, it will be excluded.
- 4. The remaining potential BL values will be categorized in the following time since onset bins: >1-2 years, >2-3 years, >3-4 years or >4-5 years.
- 5. If there are several potential BL values for the same eye in the same bin, the eye with the BL value closest to the midpoint of the bin will be selected.
- 6. The selected BL value and the follow-up VA assessment within 12±3 months in the same eye will be included in the external NH control set for the eyes in the LEROS ITT population with BL >1 year after the onset of symptoms.

The described process will be applied for the 6, 18 and 24 month time points for the eyes with BL >1 year after the onset of symptoms.

It should be noted that different cuts (various BL with corresponding follow-up VA values) from the same eye can be used multiple times, both for the analysis of the primary endpoint (only once) and for the analysis of eyes with BL>1 year after the onset of symptoms (not more than once within each of the four bins of follow-up months defined in Table 1).

9 General statistical considerations

Continuous data will be summarized using the number of observations (n), mean, standard deviation (SD), standard error of the mean (SEM), median, 1st and 3rd quartile, minimum and maximum.

Categorical data will be presented in contingency tables with frequencies and percentages.

The listings will be generally sorted by center and patient number (and by visit, if applicable).

Graphical representations will be used as appropriate.

In general, apart from the safety population, data will be summarized by onset of symptoms

- ≤ 1 year after the onset of symptoms;
- >1 year after the onset of symptoms

, as defined in section 16.

In the statistical analyses a p-value less than 0.05 will be considered as statistically significant. If not stated otherwise, all tests will be performed as two sided tests and two sided 95% confidence intervals will be produced for the treatment differences.

CRS-1, CRS-2 and LEROS data will be presented in separate listings (one per study).

Unscheduled or repeat assessments in LEROS will not be included in summary tables, but will be included in listings.

Otherwise specified, listings will be sorted by patient number and visit date.

Deviations from the statistical plan will be reported in the clinical study report, including the rationale for the deviation.

